### Exploratory analysis

Participants were enrolled during different stages of the COVID-19 pandemic. We will therefore conduct a subgroup analysis of all outcomes comparing participants included in the same phase of the pandemic. We will compare outcomes for participants included in the following periods:

1. September 2020 to January 2021 (N=1239); before the COVID-19 vaccines were widely distributed to the target population. A period characterized by increasing infection control measurements and concluding in lockdown.
2. April to December 2021 (N=438); Participants are now being vaccinated with the new coronavirus vaccines; most have had the two or three doses before enrollment. A period characterized by varying COVID-19 activity; a minimum of restrictions on society despite periodically high transmission rates (Omicron variant in the fall).

### Missing data

Participants are under follow-up for the primary outcome irrespective of missing questionnaires as this is mostly based on register data.

For the outcomes solely based on self-reported information (self-reported respiratory infections and severity of COVID-19) participants are only under follow-up during the periods where they have completed follow-up questionnaires.

### Adverse events

Adverse events will be described in terms of incidence in the groups and more thoroughly presented in a table as part of supplementary material (Table 4). Serious adverse events (SAE) will be classified as related to study drugs (possible/probable/definite) or unrelated to study drugs (unlikely/doubtful). If related, they are classified as expected/unexpected (SAR/SUSAR).

## 8.0 SUPPLEMENTARY INFORMATION

### Figures and tables

Figure 1: Flow chart, inclusion.

Table 1: Baseline characteristics.

Table 2: Results primary and secondary outcomes.

[figure not shown]
Table 3: Supplementary analyses (sex, age group, other vaccines, previous BCG, COVID-19 vaccination status at inclusion).

Table 4: Adverse events and serious adverse events.

Table 5: Short description of serious adverse events.

Figure 1: Flow chart, inclusion

## CONSORT 2010 Flow Diagram

**Table 1 Baseline characteristics**

	BCG	Placebo
Age, median (IQR)		
Sex female (%)		
Living alone (%)		
Spouse included in study (%)		
Active smoker (%)		
Previous smoker (%)		
Alcohol consumption, units per week, mean (SD)		
BMI, median (IQR)		
Chronic diseases		
Cardiovascular (%)		
Diabetes (%)		
Lung (%)		
Other (%)		
Level of education		
Low (%)		
Medium (%)		
High (%)		
Previously BCG vaccinated (%)		
Scar from BCG vaccination observed (%)		
COVID-19 vaccinated, yes (%) 		
One dose		
Two doses		
Three doses		

 COVID-19 vaccinated before enrollment.

**Table 2 Results primary and secondary outcomes**

Outcome	Number (%)		Hazard ratio (95% CI)	Absolute risk reduction (95% CI)
	BCG N=xxx	Placebo N=xxx		
Primary outcome				
Acute infection	xx (x.x)	xx (x.x)	x.xx (x.xx–x.xx)	x.x% (x.x%–x.x%)
Death	xx (x.x)	xx (x.x)	x.xx (x.xx–x.xx)	x.x% (x.x%–x.x%)
Hospitalization	xx (x.x)	xx (x.x)	x.xx (x.xx–x.xx)	x.x% (x.x%–x.x%)
Antibiotics	xx (x.x)	xx (x.x)	x.xx (x.xx–x.xx)	x.x% (x.x%–x.x%)
Doctor	xx (x.x)	xx (x.x)	x.xx (x.xx–x.xx)	x.x% (x.x%–x.x%)
Secondary outcomes				
Self-reported respiratory infection	xx (x.x)	xx (x.x)	x.xx (x.xx–x.xx)	x.x% (x.x%–x.x%)
Verified COVID-19	xx (x.x)	xx (x.x)	x.xx (x.xx–x.xx)	x.x% (x.x%–x.x%)
All-cause hospitalization	xx (x.x)	xx (x.x)	x.xx (x.xx–x.xx)	x.x% (x.x%–x.x%)

**Table 3 Supplementary analyses to explore possible effect modification by sex, age group, other vaccines, previous BCG, and COVID-19 vaccination status at inclusion.**

	Number (%)		Hazard ratio (95% CI)	Absolute risk reduction (95% CI)
	BCG N=xxx	Placebo N=xxx		
Acute infection – also where numbers permit subdivided on each of the outcomes included in the composite outcome.				
Females	xx (x.x)	xx (x.x)	x.xx (x.xx–x.xx)	x.x% (x.x%–x.x%)
Males	xx (x.x)	xx (x.x)	x.xx (x.xx–x.xx)	x.x% (x.x%–x.x%)
Age < 75	xx (x.x)	xx (x.x)	x.xx (x.xx–x.xx)	x.x% (x.x%–x.x%)
Age ≥ 75	xx (x.x)	xx (x.x)	x.xx (x.xx–x.xx)	x.x% (x.x%–x.x%)
Other vaccines received after randomization:				
Effect of intervention before other vaccines	xx (x.x)	xx (x.x)	x.xx (x.xx–x.xx)	x.x% (x.x%–x.x%)
Effect of intervention after other vaccines	xx (x.x)	xx (x.x)	x.xx (x.xx–x.xx)	x.x% (x.x%–x.x%)
Effect after other vaccines, by type of vaccine received:				
COVID vaccine	xx (x.x)	xx (x.x)	x.xx (x.xx–x.xx)	x.x% (x.x%–x.x%)
Influenza vaccine	xx (x.x)	xx (x.x)	x.xx (x.xx–x.xx)	x.x% (x.x%–x.x%)
Both vaccines	xx (x.x)	xx (x.x)	x.xx (x.xx–x.xx)	x.x% (x.x%–x.x%)
Has BCG scar 	xx (x.x)	xx (x.x)	x.xx (x.xx–x.xx)	x.x% (x.x%–x.x%)
No BCG scar 	xx (x.x)	xx (x.x)	x.xx (x.xx–x.xx)	x.x% (x.x%–x.x%)
CoV vaccinated before enrollment:				
Yes	xx (x.x)	xx (x.x)	x.xx (x.xx–x.xx)	x.x% (x.x%–x.x%)
No	xx (x.x)	xx (x.x)	x.xx (x.xx–x.xx)	x.x% (x.x%–x.x%)
Included period 1 	xx (x.x)	xx (x.x)	x.xx (x.xx–x.xx)	x.x% (x.x%–x.x%)
Included period 2 	xx (x.x)	xx (x.x)	x.xx (x.xx–x.xx)	x.x% (x.x%–x.x%)

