### Objectives and hypothesis

Primary objective: To reduce senior citizens' risk of acute infection during the COVID-19 pandemic.

Secondary objectives: To reduce senior citizens' risk of SARS-CoV-2 infection during the COVID-19 pandemic and to reduce self-reported respiratory illness in general during the COVID-19 pandemic.

The hypothesis is that BCG vaccination of seniors will reduce the risk of acute infection by 25% over a period of 12 months.

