### **Sample size**

With an expected incidence of “acute infection” of 20% we will be able to show a 25% reduction in the risk of acute infection in the intervention group compared to the placebo group by including a total of 1890 individuals: 945 individuals in each group. Since the primary outcome data to a large extent are obtained via national registers, we anticipate limited loss of power due to loss to follow-up. We therefore aimed to enroll 1900 participants.

Due to the pandemic and varying infectious disease precautions, recruitment took longer than anticipated, and we ended up recruiting a total of 1706 participants (90% of the anticipated sample size) between September 2020 and December 2021.

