## **4.0 STATISTICAL PRINCIPLES**

### **Levels of confidence and p-values**

A double-sided p-value of  $< 0.05$  will be considered statistically significant. 95% confidence intervals will be provided.

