#### **Supplementary analyses**

We will conduct preplanned supplementary analyses to assess possible effect modification by other vaccines given during follow-up, previous BCG vaccination, and COVID-19 vaccination before inclusion. These will be done using the same methods as described above for the primary (composite) outcome and for all secondary outcomes.

1. Before and after receipt of subsequent vaccines, and adjusted by type of subsequent vaccine, to assess possible interaction between BCG and other vaccines. Vaccination status will be categorized as 1) No other vaccines, 2) COVID 19 vaccine, 3) Influenza vaccine, or 4) COVID 19 and influenza vaccine.

Vaccination status will be included as a time varying covariate changing on the date of vaccination with subsequent vaccines received during follow-up. Some participants received a pneumococcal vaccine (23-valent polysaccharide vaccine) together with their influenza vaccine as was recommended by the Danish Board of Health in 2020. We will therefore include influenza vaccines with or without concurrent pneumococcal vaccination (given on the same day). Participants will be censored upon receipt of any other vaccines than the above mentioned.

2. By previous BCG vaccination (Yes/no, self-reported and assessed by BCG scar) to assess the effect of revaccination vs. first vaccination with BCG.

3. By COVID-19 vaccination status at inclusion (Received COVID 19 vaccines yes/no).

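### In Part A Table 3, the rows split at receipt of other vaccines report percentages and absolute risk reductions that depend on time spent in each state, with no denominator or horizon fixed

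*SAP*

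**What the plan says.** Part A, section 7.0, Supplementary analyses, item 1, plans to examine the BCG effect before and after other vaccines and by type of vaccine. It states: "Vaccination status will be included as a time varying covariate changing on the date of vaccination with subsequent vaccines received during follow-up". One participant can thus contribute time to the 'before' state and then to an 'after' state, and can move from one vaccine type to both. Receipt of any vaccine outside the listed types censors follow-up.

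Table 3 in section 8.0 has five rows of this kind for each outcome: before other vaccines, "Effect of intervention after other vaccines", and after COVID-19 vaccine, influenza vaccine or both. They share their columns with the rows for sex, age, BCG scar and inclusion period: number (%), hazard ratio and absolute risk reduction as a percentage. The header shows one N per arm. The shell contains no person-time, rate, row-specific denominator or horizon.

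Section 7.0, Primary outcome, says only that absolute risk reductions come from Cox regression. The SAP does not report when participants received other vaccines.

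**The concern.** A percentage with an event needs a defined set of people observed for a defined period. A baseline subgroup has both. A time-varying state has neither: people enter it at different times, some never enter it, and the time spent in it differs from the time spent outside it. The proportion with an event grows with the length of the window, and so does a risk difference taken over that window.

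Table 3 is meant to explore effect modification, and these rows are the ones that address interaction between BCG and other vaccines. Readers will compare 'before' with 'after'. If the absolute columns differ because the windows differ, the table suggests an interaction where there may be none, or hides one. Without person-time in the table, a reader cannot tell which.

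**Working it through.** **Inputs from the SAP**
- Placebo risk of acute infection: 20% (section 3.0, Sample size).
- Effect: "25% reduction in the risk of acute infection in the intervention group compared to the placebo group", so 20% versus 15%.
- Horizon: the hypothesis in section 2.0 is that BCG "will reduce the risk of acute infection by 25% over a period of 12 months". The 20% is therefore read as a 12-month risk.

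**Check of these inputs against the plan's own figure.** Take 20% versus 15%, two-sided alpha 0.05 and 80% power (power is not stated in Part A, so this is an assumption). The uncorrected formula for two proportions gives

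n = [1.960·√(2·0.175·0.825) + 0.842·√(0.20·0.80 + 0.15·0.85)]² / 0.05² ≈ 905.4, i.e. 906 per group.

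The continuity correction, (n/4)·[1 + √(1 + 4/(n·0.05))]², gives 945, which matches "945 individuals in each group". The sample size is not in dispute; the match only confirms the inputs.

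**Assumptions not in the SAP:** constant hazard, constant hazard ratio of 0.75, first events only, and everyone vaccinated at the same month v, varied from 1 to 11.

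**Formulas**
- Monthly placebo hazard: λ = −ln(0.80)/12 = 0.0186.
- Risk over a window of t months: 1 − exp(−λt) on placebo and 1 − exp(−0.75λt) on BCG.
- 'Before' has t = v; 'after' has t = 12 − v. The risk reduction is the difference between arms within each window.

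For v = 4, placebo risk is 7.17% before and 13.82% after; BCG risk is 5.43% and 10.56%. Risk reductions for a range of v (ratios use unrounded values):

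| Vaccination month v | Reduction before (points) | Reduction after (points) | Ratio after/before |
|---|---|---|---|
| 1 | 0.46 | 4.28 | 9.35 |
| 2 | 0.90 | 3.95 | 4.39 |
| 3 | 1.33 | 3.61 | 2.72 |
| 4 | 1.74 | 3.27 | 1.87 |
| 6 | 2.53 | 2.53 | 1.00 |
| 8 | 3.27 | 1.74 | 0.53 |
| 9 | 3.61 | 1.33 | 0.37 |
| 11 | 4.28 | 0.46 | 0.11 |

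A ratio of exactly 2 needs vaccination at about month 3.8. If vaccination times are instead spread exponentially with mean 3, 4, 6 or 9 months, and the 'after' denominator is those vaccinated within 12 months, the ratio is 2.92, 2.17, 1.50 or 1.11.

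**What does not move under the same assumptions**
- Hazard ratio: 0.75 in both rows for every v.
- Rate difference: 12·λ·(1 − 0.75) = 0.0558 per person-year, or 5.58 per 100 person-years, in both rows.
- Risk reduction at a common 12-month horizon: 0.80^0.75 − 0.80 = 4.59 points in both rows.

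**Extent.** Five rows for each of four outcomes make 20 table lines with undefined absolute columns. The numerical illustration covers only the before/after pair for acute infection.

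**The case against.** The strongest defence is that the SAP does not tell the analyst to use unequal windows. Risk reductions are model-based, and at a common horizon they would agree under a constant effect (4.59 points in both rows). The single N per arm is also a generic header: the sex and age rows plainly need their own denominators too, so the shell need not mean a percentage of the whole arm. Both points are fair, and the correct charge is that denominator and horizon are left open. They do not rescue the columns. A percentage for a time-varying state depends on time in that state under any denominator of persons. A 12-month 'after' risk describes someone in that state from day 0, whereas the state is entered during a follow-up that lasts 12 months; it would be an extrapolation and should be labelled as one.

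A reader might infer that BCG will look about twice as effective after other vaccines, because people spend less time before vaccination than after it. The SAP does not support this. It gives no vaccination dates, and section 7.0, Exploratory analysis, describes two differing cohorts: 1239 enrolled before wide COVID-19 vaccine roll-out, and 438 of whom most were already vaccinated at entry. No single split can be read from that, and the ratio reverses once vaccination falls after month 6.

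It is also fair that the hazard ratio in the same rows is sound, and that rates are not a perfect remedy. At a constant hazard ratio of 0.75, the rate difference is 0.25 times the placebo rate, so a doubled background rate would double it (5.58 to 11.16 per 100 person-years). The SAP itself describes changing restrictions and transmission.

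**Conclusion.** The point holds for two columns of the time-split rows. The percentage has no defined denominator or period and the absolute risk reduction has no horizon, so both can differ between rows when BCG acts equally in each.

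The distortion cannot be sized from the SAP. Evaluated over each row's own window, the ratio runs from about 9 (month 1) through 1.0 (month 6) to about 0.1 (month 11). This rests on a 20% 12-month placebo risk, a constant hazard, a constant hazard ratio of 0.75 and first events, whereas acute infection and self-reported respiratory infection are to be analysed as recurrent events.

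The hazard ratios are not affected and neither is the primary result. Correcting the rows is worthwhile because they are the pre-specified ones for interaction with other vaccines.

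**What to change.** For the five time-split rows of each outcome in Part A Table 3:
- replace number (%) with events / person-years and the rate per 100 person-years in each arm;
- replace the absolute risk reduction with the rate difference per 100 person-years and a 95% CI that accounts for clustering within couples and, where the outcome is recurrent, for repeated events in one person;
- keep the hazard ratio and name it as the measure on which interaction is judged;
- add a footnote that rate differences also reflect changes in background incidence between the periods compared.

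The cost is a change to the table shell and some programming. The time-varying Cox model already needs the split person-time. The small downside is that the absolute columns of these rows are no longer on the same scale as the rest of the table.

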**Self-reported respiratory infection**

Females	xx (x.x)	xx (x.x)	x.xx (x.xx–x.xx)	x.x% (x.x%–x.x%)
Males	xx (x.x)	xx (x.x)	x.xx (x.xx–x.xx)	x.x% (x.x%–x.x%)
Age < 75	xx (x.x)	xx (x.x)	x.xx (x.xx–x.xx)	x.x% (x.x%–x.x%)
Age ≥ 75	xx (x.x)	xx (x.x)	x.xx (x.xx–x.xx)	x.x% (x.x%–x.x%)
Other vaccines received after randomization:				
Effect of intervention before other vaccines	xx (x.x)	xx (x.x)	x.xx (x.xx–x.xx)	x.x% (x.x%–x.x%)
Effect of intervention after other vaccines	xx (x.x)	xx (x.x)	x.xx (x.xx–x.xx)	x.x% (x.x%–x.x%)
Effect after other vaccines, by type of vaccine received:				
COVID vaccine	xx (x.x)	xx (x.x)	x.xx (x.xx–x.xx)	x.x% (x.x%–x.x%)
Influenza vaccine	xx (x.x)	xx (x.x)	x.xx (x.xx–x.xx)	x.x% (x.x%–x.x%)
Both vaccines	xx (x.x)	xx (x.x)	x.xx (x.xx–x.xx)	x.x% (x.x%–x.x%)
Has BCG scar 	xx (x.x)	xx (x.x)	x.xx (x.xx–x.xx)	x.x% (x.x%–x.x%)
No BCG scar 	xx (x.x)	xx (x.x)	x.xx (x.xx–x.xx)	x.x% (x.x%–x.x%)
CoV vaccinated before enrollment:				
Yes	xx (x.x)	xx (x.x)	x.xx (x.xx–x.xx)	x.x% (x.x%–x.x%)
No	xx (x.x)	xx (x.x)	x.xx (x.xx–x.xx)	x.x% (x.x%–x.x%)
Included period 1 	xx (x.x)	xx (x.x)	x.xx (x.xx–x.xx)	x.x% (x.x%–x.x%)
Included period 2 	xx (x.x)	xx (x.x)	x.xx (x.xx–x.xx)	x.x% (x.x%–x.x%)

**Verified COVID-19**

Females	xx (x.x)	xx (x.x)	x.xx (x.xx–x.xx)	x.x% (x.x%–x.x%)
Males	xx (x.x)	xx (x.x)	x.xx (x.xx–x.xx)	x.x% (x.x%–x.x%)
Age < 75	xx (x.x)	xx (x.x)	x.xx (x.xx–x.xx)	x.x% (x.x%–x.x%)
Age ≥ 75	xx (x.x)	xx (x.x)	x.xx (x.xx–x.xx)	x.x% (x.x%–x.x%)

Other vaccines received after randomization:				
Effect of intervention before other vaccines	xx (x.x)	xx (x.x)	x.xx (x.xx–x.xx)	x.x% (x.x%–x.x%)
Effect of intervention after other vaccines	xx (x.x)	xx (x.x)	x.xx (x.xx–x.xx)	x.x% (x.x%–x.x%)
Effect after other vaccines, by type of vaccine received:				
COVID vaccine	xx (x.x)	xx (x.x)	x.xx (x.xx–x.xx)	x.x% (x.x%–x.x%)
Influenza vaccine	xx (x.x)	xx (x.x)	x.xx (x.xx–x.xx)	x.x% (x.x%–x.x%)
Both vaccines	xx (x.x)	xx (x.x)	x.xx (x.xx–x.xx)	x.x% (x.x%–x.x%)
Has BCG scar 	xx (x.x)	xx (x.x)	x.xx (x.xx–x.xx)	x.x% (x.x%–x.x%)
No BCG scar 	xx (x.x)	xx (x.x)	x.xx (x.xx–x.xx)	x.x% (x.x%–x.x%)
CoV vaccinated before enrollment:				
Yes	xx (x.x)	xx (x.x)	x.xx (x.xx–x.xx)	x.x% (x.x%–x.x%)
No	xx (x.x)	xx (x.x)	x.xx (x.xx–x.xx)	x.x% (x.x%–x.x%)
Included period 1 	xx (x.x)	xx (x.x)	x.xx (x.xx–x.xx)	x.x% (x.x%–x.x%)
Included period 2 	xx (x.x)	xx (x.x)	x.xx (x.xx–x.xx)	x.x% (x.x%–x.x%)
All-cause hospitalization				
Females	xx (x.x)	xx (x.x)	x.xx (x.xx–x.xx)	x.x% (x.x%–x.x%)
Males	xx (x.x)	xx (x.x)	x.xx (x.xx–x.xx)	x.x% (x.x%–x.x%)
Age < 75	xx (x.x)	xx (x.x)	x.xx (x.xx–x.xx)	x.x% (x.x%–x.x%)
Age ≥ 75	xx (x.x)	xx (x.x)	x.xx (x.xx–x.xx)	x.x% (x.x%–x.x%)
Other vaccines received after randomization:				
Effect of intervention before other vaccines	xx (x.x)	xx (x.x)	x.xx (x.xx–x.xx)	x.x% (x.x%–x.x%)
Effect of intervention after other vaccines	xx (x.x)	xx (x.x)	x.xx (x.xx–x.xx)	x.x% (x.x%–x.x%)

Effect after other vaccines, by type of vaccine received:				
COVID vaccine	xx (x.x)	xx (x.x)	x.xx (x.xx–x.xx)	x.x% (x.x%–x.x%)
Influenza vaccine	xx (x.x)	xx (x.x)	x.xx (x.xx–x.xx)	x.x% (x.x%–x.x%)
Both vaccines	xx (x.x)	xx (x.x)	x.xx (x.xx–x.xx)	x.x% (x.x%–x.x%)
Has BCG scar 	xx (x.x)	xx (x.x)	x.xx (x.xx–x.xx)	x.x% (x.x%–x.x%)
No BCG scar 	xx (x.x)	xx (x.x)	x.xx (x.xx–x.xx)	x.x% (x.x%–x.x%)
CoV vaccinated before enrollment:				
Yes	xx (x.x)	xx (x.x)	x.xx (x.xx–x.xx)	x.x% (x.x%–x.x%)
No	xx (x.x)	xx (x.x)	x.xx (x.xx–x.xx)	x.x% (x.x%–x.x%)
Included period 1 	xx (x.x)	xx (x.x)	x.xx (x.xx–x.xx)	x.x% (x.x%–x.x%)
Included period 2 	xx (x.x)	xx (x.x)	x.xx (x.xx–x.xx)	x.x% (x.x%–x.x%)

 Scar from previous BCG vaccination at enrollment.

 Period 1: September 2020 to January 2021 (N=1239); before the COVID-19 vaccines were widely distributed to the target population. A period characterized by increasing infection control measurements and concluding in lockdown.

 Period 2: April to December 2021 (N=438); Participants are now being vaccinated with the new coronavirus vaccines; most have had the two or three doses before enrollment. A period characterized by varying COVID-19 activity; a minimum of restrictions on society despite periodically high transmission rates (Omicron variant in the fall).

**Table 4 Adverse Events (AE) and Serious Adverse Events (SAE)**

Endpoint	BCG	Placebo
	Number (%) [M/F]	Number (%) [M/F]
Any SAE		
Hospitalization for any reason		
Death due to any reason		
Adverse events (AE):		
Injection site reaction		
Minor abscess/wound		
Severe local reaction (abscess)		
Fever		
Fatigue		
Headache		
Lymphadenitis		
Serious Adverse Events (SAE):		
Blood or lymphatic disorder		
Cardiac disorders		
Endocrine disorders		
Gastrointestinal disorders		
Infection		
Musculoskeletal and connective tissue disorders		
Nervous system disorders		
Respiratory disorders		

Urological and gynecological disorders		
Unknown/other		
Outcome SAE:		
Life threatening		
Required/prolonged hospitalization		
Resulted in death		

**Table 5 Short description of Serious Adverse Events (SAE)**

No	Category	Outcome	Description	Group 	Sex	Week 	Before/after 
1							
2							
3							
4							
5							
6							
7							
8							
9							
10							

Randomisation group.Weeks after inclusion.Occurrence before or after other vaccines were administered to the participant.

## 2.0 INTRODUCTION

### Background

Severe influenza virus infections are more common in the elderly and seasonal vaccination with inactivated influenza vaccine (IIV) is recommended to persons above 65 years of age. However, due to immunosenescence, the efficacy of vaccines decrease with increasing age.

The Bacille Calmette Guérin vaccine (BCG) was developed for tuberculosis prevention, but there is increasing evidence that it also has beneficial heterologous “non-specific” effects on the immune system. Prior studies have shown that BCG vaccine strengthens the innate immune system resulting in increased activity against non-related infections. A potentiating effect of BCG vaccine on the response to other vaccines has also been observed in previous studies.

In the present project, we will explore BCG as a low-cost, low-risk intervention to increase the immune response to influenza vaccination and improve the general resistance towards infections in senior citizens.

### Objectives and hypothesis

We will test the effects of BCG vaccination on the specific immune response to IIV and on the immune system and health in general in people  $\geq 65$  years, with the aim to:

- Improve their specific antibody response to influenza vaccination.
- Improve their general resistance towards infections.
- Study the effect of BCG on classical lymphocyte-dependent responses, and the induction of innate immune memory.

We will test the following hypotheses:

- a) BCG vaccine given two weeks prior to, together with, or two weeks after IIV is associated with a 30% increase in seroconversion to IIV and/or a significant increase in influenza antibody titers.
- b) The hypothesized potentiating effects of BCG is due to a combination of classical lymphocyte-dependent responses, and the induction of innate immune memory (trained

immunity) in myeloid cells.

## 10.0 STUDY METHODS

### Trial design

A single-blinded, placebo controlled, randomized clinical trial, with nested immunological studies. Participants are randomized 1:1:1:1 to four groups: BCG 14 days before, together with, or 14 days after IIV compared to placebo.

People  $\geq 65$  years of age who plan to accept the offer of seasonal influenza vaccination are eligible for participation.

Participants are vaccinated once at day 0 and twice at day 14 (one shot in each arm). All participants receive the standard seasonal IIV recommended by the Danish Board of Health. The participants will come back for a follow-up interview at day 42 and all are followed for six months post-randomization with electronic questionnaires about their health. These include information on symptoms and disease, potential side effects, other vaccinations, visits to general practitioner or on call doctor, and hospitalizations. Every survey period is 14 days, starting from day 0 (inclusion).

Blood samples for influenza antibody testing are collected from all participants at day 14 and 42. Samples for further immunological analyses are collected from subgroups at day 0, day 14, day 21, and day 42.

Vaccination schedule:

Group	Day 0 (one shot)	Day 14 (two shots)	Day 42
1	BCG	IIV + Placebo	Follow up visit
2 (Control)	Placebo	IIV + Placebo	Follow up visit
3	Placebo	IIV + BCG	Follow up visit
4	IIV	Placebo + BCG	Follow up visit

